10 PRESENTATION OF SAFETY DATA

Safety data will be collected for all randomized participants from the time of randomization through day 28 unless the participant withdraws from the study before day 28. The information to be collected on safety-related events includes event narratives, investigator-assigned likelihood of relatedness to study treatments (unlikely, possibly, probably), distinctions between serious and non-serious adverse events, expectedness of the event, and the event outcome. Event severity will be classified using the Common Terminology Criteria for Adverse Events (CTCAE) v3.0. Tabulations of these data will be performed in the intention to treat population using the treatment groups defined in Section 5.1. Safety data will be tabulated by treatment group and will include the following.

- Frequency and percentage of serious adverse events (SAEs) overall, by treatment group, and by various cross classifications of treatment group, CTCAE classification, expectedness, relatedness to study treatments, and outcome.
- Frequency and percentage of all-cause study drug discontinuation overall and by treatment group
- Frequency and percentage of each of the following adverse events of special interest (EOSI) overall and by treatment group:
 - Arrhythmias (ventricular), not including torsade de pointes
 - Torsade de pointes
 - Hepatic Failure
 - Bone marrow failure
 - Aplastic anemia
 - Prolonged QT interval
 - Angioedema
 - Exfoliative dermatitis
 - Acute generalized exanthematous pustulosis (AGEP)

- Psychosis
- Suicidal Ideation
- Seizure
- Narrative descriptions of unanticipated problems
- Patient- and event-level listings and additional tabulations as requested by the DSMB

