3 STUDY DESIGN AND OBJECTIVES

PROTECT is an open-label, factorial randomized clinical trial with two factors and nested randomization. Patients hospitalized with confirmed SARS-CoV-2 infection will be initially randomized to one of two arms in a 1:1 ratio: 1) Standard of care treatment or 2) Standard of care treatment plus 5 days of hydroxychloroquine (HCQ). Patients with no contraindication to azithromycin (AZM) who have not received AZM in the seven days prior to enrollment will undergo a second randomization in a 1:1 ratio to either receive 1) No AZM or 2) 5 days of AZM. The resulting treatment group combinations are summarized in Table 1. Participants will be followed for 28 days after randomization or until hospital discharge, whichever is later. The primary endpoint is the World Health Organization (WHO) ordinal scale for clinical improvement as measured on day 14 after randomization (see Section 6.1 for details).

Table 1. Treatment groups

	AZM: No	AZM: Yes	AZM: Not Eligible
HCQ: No	Group 1: SOC	Group 3: SOC + AZM	Group 5: SOC, AZM-ineligible
HCQ: Yes	Group 2: SOC + HCQ	Group 4: SOC + HCQ + AZM	Group 6: SOC + HCQ, AZM-ineligible

HCQ = hydroxychloroquine, AZM = azithromycin, SOC = standard of care

Hypothesis #1 (HCQ versus no HCQ): Groups 2+4+6 versus 1+3+5

Hypothesis #2 (AZM versus no AZM): Groups 3+4 versus 1+2

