5 POPULATIONS FOR EFFICACY AND SAFETY ANALYSES

5.1 Intention-to-treat population

The intention-to-treat (ITT) population will include all participants who receive a randomized treatment assignment, including those who are later determined not to meet trial eligibility criteria, unless the randomization was an unintentional administrative error, as determined by the coordinating center at the Duke Office of Clinical Research. Patients will be assigned to treatment groups based on each patient's randomized treatment group assignment regardless of which treatment if any the patient actually received.

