7 GENERAL ANALYSIS CONSIDERATIONS

Analyses will be performed according to the principle of "intention-to-treat" with subjects analyzed (and endpoints attributed) according to the group to which enrolled subjects were randomized, regardless of subsequent medications or treatment crossover. All major treatment group comparisons will be performed using Bayesian statistical methods. The output of a Bayesian analysis is a posterior probability distribution describing the relative likelihood of different numerical estimates for unknown quantities. This posterior distribution can be used to determine the likelihood of a clinically important treatment benefit or harm in light of the study data. The Bayesian approach provides an especially useful perspective for interpreting results of small studies that are likely to be accompanied by substantial statistical uncertainty. The Bayesian analog of a confidence interval, known as a credible interval, has a direct and intuitively appealing interpretation as an interval containing the true value with a specified probability. Point estimates will be calculated as posterior means and accompanied with 95% equal-tailed credible intervals. Analysis results will also be framed in terms of probability statements, for example, the probability that the study drugs lead to improved outcomes on the primary endpoint. The analysis plan does not include frequentist hypothesis testing and does not make adjustment for multiple comparisons. Additional considerations related to multiple comparisons are discussed in Sections 11.1.

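### Every pre-specified safety table follows randomized assignment in the ITT population; no table by drug actually received is defined, and administrative-error randomizations fall out of all of them

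*SAP*

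**What the plan says.** SAP Section 5 is headed "POPULATIONS FOR EFFICACY AND SAFETY ANALYSES", but it defines only the intention-to-treat population. Section 5.1 places each patient by "randomized treatment group assignment regardless of which treatment if any the patient actually received". It keeps patients later found ineligible and leaves out a randomized patient only under one exception: "unless the randomization was an unintentional administrative error, as determined by the coordinating center".

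Section 10 collects safety information on everyone randomized, through day 28 unless they withdraw. It then states: "Tabulations of these data will be performed in the intention to treat population using the treatment groups defined in Section 5.1". The tables listed include serious adverse events with several cross-classifications, study drug discontinuation, and events of special interest such as prolonged QT, torsade and ventricular arrhythmia. Patient- and event-level listings, and further tables that the DSMB may ask for, are also mentioned.

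Two features of the design bear on this. Section 3 states: "PROTECT is an open-label, factorial randomized clinical trial with two factors and nested randomization". Section 7 analyses patients as randomized "regardless of subsequent medications or treatment crossover". Section 3 also limits the second randomization to "Patients with no contraindication to azithromycin (AZM) who have not received AZM in the seven days prior to enrollment"; everyone else goes to groups 5 and 6.

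**The concern.** For efficacy, analysis by assignment is the natural primary choice, and any shrinkage of the effect is usually accepted as conservative. For harm it works the other way: if assigned and received treatment diverge, a drug-related excess looks smaller than it is among patients who took the drug. A control patient given open-label HCQ who then has an arrhythmia is counted under standard of care. A patient assigned HCQ who never takes it stays in the HCQ denominator.

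The special-interest list includes QT prolongation and ventricular arrhythmia, where actual exposure, above all to both drugs together, is an obvious question for the DSMB and for readers of the final report. No planned table answers it.

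The second issue is coverage. Because ITT is the only population, anyone removed from it is also removed from the safety tables. A patient randomized in error who received study drug and had an event would have data collected under Section 10 but would be counted nowhere.

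**Working it through.** The SAP gives no adherence, crossover or adverse event rate, so there is no figure to reproduce. The check has three parts.

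**1. Size of the shrinkage, if assignment and receipt differ.** Let p1 be the event risk with the drug, p0 the risk without it, a the share of the drug arm not exposed and c the share of the no-drug arm exposed. Assume that risk depends only on receipt of the drug. Then

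- drug arm as tabulated = (1 - a)·p1 + a·p0
- no-drug arm as tabulated = (1 - c)·p0 + c·p1
- difference = (p1 - p0)·(1 - a - c)

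The proportion of the difference that survives does not depend on p1 or p0. With assumed risks p1 = 15% and p0 = 5% (true difference 10.0 points, ratio 3.00):

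| a | c | Drug arm | No-drug arm | Difference (points) | Factor | Ratio |
|---|---|---|---|---|---|---|
| 0% | 0% | 15.0% | 5.0% | 10.0 | 1.00 | 3.00 |
| 5% | 5% | 14.5% | 5.5% | 9.0 | 0.90 | 2.64 |
| 10% | 10% | 14.0% | 6.0% | 8.0 | 0.80 | 2.33 |
| 20% | 20% | 13.0% | 7.0% | 6.0 | 0.60 | 1.86 |
| 20% | 30% | 13.0% | 8.0% | 5.0 | 0.50 | 1.63 |

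A second assumed pair, 10% and 3%, behaves the same way. With a = 10% and c = 20% the table would show 9.3% against 4.4%, a difference of 4.9 = 7.0 × 0.70 points.

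**2. Recent AZM users in groups 5 and 6.** Prior AZM is fixed before randomization, and the stratum is randomized 1:1, so the share q of recent users is expected to be equal in the two groups. Assume a 5% baseline risk, +5 points for HCQ and +3 for recent AZM.

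- Additive effects: group 5 = 5 + 3q and group 6 = 10 + 3q. The difference is 5.0 points for every q from 0 to 1; the ratio falls from 2.00 to 1.62.
- With a further 5 points when both drugs are present: group 6 = 10 + 8q. The difference is 5 + 5q, rising from 5.0 to 10.0.

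Under these assumptions recent AZM does not shrink the HCQ risk difference and may enlarge it. It also cannot touch the AZM comparison, which uses groups 3+4 against 1+2. What remains is that no planned table separates patients with a contraindication from those with recent AZM, so patients in group 6 with recent AZM plus HCQ cannot be identified.

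**3. Coverage.** Safety data are collected on all randomized participants (Section 10). They are tabulated in ITT (Section 10). ITT leaves out administrative-error randomizations (Section 5.1). It follows that these participants' events are collected and not tabulated.

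**The case against.** Tables by assignment are a legitimate safety analysis, and they alone preserve the randomized comparison. In an open-label trial, who receives or is spared a drug may depend on prognosis, so an as-treated comparison can mislead in either direction. This stands: the ITT tables should remain, and any exposure-based set is supportive.

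Section 10 is also wider than its fixed tables. It provides relatedness cross-classifications, drug discontinuation by group, listings, and extra tables if the DSMB asks; Section 11 has protocol compliance under interim review. A DSMB that looks for off-protocol exposure can probably find it. That softens the gap without closing it: none of these outputs is specified by drug received, and the discontinuation table says nothing about controls who were given the drug.

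A reader might infer that dilution is already established. The documents do not support that: the Section 7 wording is ordinary ITT language, no rate is given, and with complete adherence the two sets of tables coincide. A reader might also infer that recent AZM users are counted as patients without AZM, or that they add to the dilution. Table 1 in Section 3 gives groups 5 and 6 their own not-eligible column, the model in Section 8.3 codes them separately, and part 2 of the check shows no loss in the HCQ risk difference.

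The administrative-error exclusion is narrow and probably affects few patients. That limits its size, but the inconsistency remains.

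**Conclusion.** The point holds in limited form. All pre-specified safety tables are by assignment, none is by drug received, and the only population under a heading that promises safety populations is ITT. Any understatement of drug-related differences is conditional. It equals the factor (1 - a - c), which is 0.90 at 5%/5%, 0.80 at 10%/10% and 0.60 at 20%/20%, and 1 if there is neither non-adherence nor crossover. All these shares are assumed, and the factor also requires that risk depends only on receipt; the size in this trial cannot be known from the SAP. The loss of administrative-error randomizations from the tables follows directly from the text, with unknown frequency. The mixture within groups 5 and 6 is a labelling matter only. This is an inexpensive improvement worth making; the planned ITT tables are not invalid.

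**What to change.** 1. Keep the ITT safety tables as they are.
2. In Sections 5 and 10, define a supportive safety population of all randomized participants with follow-up, including administrative-error randomizations, classified by what was actually received after randomization: neither drug, HCQ only, AZM only, or both. Off-protocol use counts as receipt.
3. Produce the serious adverse event and special-interest event tables on this population for the DSMB reviews and the final report.
4. As a descriptive display, show groups 5 and 6 split by reason for AZM ineligibility: contraindication, or AZM in the seven days before enrollment.

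The cost is a few sentences in the SAP and one more set of tables. It also requires that HCQ and AZM use after randomization be recorded in every group, which the SAP alone does not let us confirm. Comparisons by treatment received are not protected by randomization, so the new tables should be labelled supportive and read beside the ITT tables.

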11 INTERIM ANALYSES

The primary objective of interim analyses is to ensure the safety of the participants enrolled in the trial and to evaluate the accumulating safety and efficacy data by treatment group to test for possible differences favoring any of the randomized treatments or treatment combinations. In addition, interim monitoring will involve a review of participant recruitment, compliance with the study protocol, status of data collection, an assessment of whether control group event rates are consistent with the rates hypothesized in the sample size calculations, and other factors which reflect the overall progress and integrity of the study including potential geographic differences.

An independent DSMB will review safety data on a regular basis according to the schedule specified in the DSMC charter. A team of one or two independent statisticians (i.e., the DSMB reporting statisticians) will be the only individuals (aside from the DSMB) with knowledge of interim outcomes by treatment group. Safety listings and tabular summaries will be generated regularly for the DSMB review. Unplanned meetings may be called if the DSMB members deem it to be necessary. The frequency of generating/sending these tables and listings to the DSMB is specified in the DSMC Charter.

Interim efficacy analyses will focus on the primary endpoint (World Health Organization ordinal scale) and death during the index hospitalization. Analyses will be performed both for the comparison of hydroxychloroquine versus no hydroxychloroquine (Hypothesis #1) and for the comparison of azithromycin versus no azithromycin (Hypothesis #2). The first pre-planned interim review of efficacy data will be performed after completion of data collection for the primary endpoint of the first 75 participants and subsequent pre-planned efficacy reviews will be performed approximately bi-weekly or based on a schedule specified in the DSMB charter. Considerations for multiple testing of the accumulating trial data are discussed in Section 11.1.

Statistical methods for interim analyses will be identical to those described in Section 8 for the final analysis. For the WHO scale primary endpoint, the statistical framework will be a Bayesian parametric win ratio analysis based on the proportional odds model. For mortality, the statistical framework will be a Bayesian logistic regression analysis. Guidelines proposed to the DSMB for interpretation of interim results are summarized in Table 5:

Table 5. Proposed guidelines for DSMB statistical monitoring

	Definition	Monitoring Guideline
Moderate efficacy.	Win Ratio ≥ 1.25 favoring study drug over no study drug	Signal if probability is $>80\%$
Any efficacy	Win Ratio >1.0 favoring study drug over no study drug	Signal if probability is $>95\%$

Inefficacy	Win Ratio <1.0 favoring no study drug over study drug	Signal if probability is >80%
Moderate harm	Win Ratio <0.9 favoring no study drug over study drug	Signal if probability is >75%

Note: Study drug refers to the comparison of HCQ versus no HCQ (hypothesis #1) or the comparison of AZM versus no AZM (hypothesis #2). Win ratios will be estimated for both the primary endpoint and death during the index hospitalization.

11.1 Multiplicity considerations for interim analyses

The repeated analysis of multiple endpoints across multiple time points gives rise to the possibility of drawing an incorrect conclusion as a result of the play of chance. Based on Monte Carlo simulations performed during protocol development, we estimate that the probability of a signal occurring for moderate or any efficacy if outcomes are monitored continuously across 500 patients and there is truly no between group difference in the primary endpoint is 14%. The Bayesian approach to controlling the probability of an incorrect conclusion involves selecting a prior distribution that faithfully reflects the user's prior degree of skepticism concerning the possibility of a clinically meaningful treatment benefit or harm. If the Bayesian prior distribution is well calibrated to the user's degree of skepticism, then the calculated posterior probabilities are appropriate to use for decision making without the requirement for a multiple comparisons adjustment. Although we have specified a set of guidelines for monitoring by the DSMB, we do not specify a degree of Bayesian certainty that should be regarded as "definitive evidence" at the end of the trial. Instead, we assume that stakeholders will use the calculated probabilities to inform their decision making and that different users may apply different thresholds for determining whether the degree of certainty is sufficient to warrant any particular conclusion or action based on the data.

